## 7. Statistical Plan

### 7.1. Power

A power analysis is provided only for the primary aims because the exploratory aim is hypothesis generating. Most of our power calculations were approximated as 2-sided t- or z-tests, with  $\alpha = 0.05$ , using PASS Software (Power and Sample Size, NCSS Software, Kaysville, UT). Equivalence testing was approximated as two one-sided tests, with  $\alpha = 0.025$  each.

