#### 7.1.1. Aim 1:

The primary efficacy analysis (**H1**) is a comparison in week 10 (of treatment) and week 24 post-TQD of CO-confirmed 7-day point prevalence quit rates for the placebo and bupropion groups. For the week-10 comparison, we expect that the quit rates in the placebo and bupropion arms would approximate those reported in bupropion trials in the general population of smokers (i.e., placebo = 21.2%; bupropion = 35.9%, OR = 2.1; ref. 44). A sample of 360 provides 88% power to detect a significant between-group effect. The OR for bupropion treatment is similar at 24 weeks, based on Jorenby et al. (168) and our own data, and results from 10 and 24 weeks are highly correlated ( $\rho > 0.7$ ). Thus, we have 80% power to detect a significant difference between treatment arms.

Safety analyses (**H2**) will examine maternal safety across the 10-week treatment and 24-week follow-up periods and fetal and birth outcomes. Key maternal and fetal outcomes to be compared across treatment groups include rates of moderate-to-severe side AEs of bupropion (from the AE checklist). Key birth outcomes will include Apgar scores, birth weight, duration of pregnancy, rate of obstetrical complications, and need for NICU admission. These analyses will involve a test of equivalence because we cannot use standard statistical tests to conclude that a non-significant comparison shows that the drug is safe (i.e., "the absence of evidence is not evidence of its absence"). In our past study with bupropion, 45% of bupropion-treated participants reported no moderate-to-severe AEs, vs. 47% of participants on placebo, a 2% difference. With the present sample size, we will have 82% power to detect similar equivalence between treatment arms on the frequency of moderate-to-severe AEs over the course of the trial, given that AEs are not significantly different between treatment arms, using an equivalence window of 0.30 to 0.60. Likewise, Oncken et al. (47) reported 38% AEs for the placebo group

CONFIDENTIAL

and 25% in the nicotine group. An equivalence test with placebo and bupropion groups both at 30% and an equivalence window for bupropion of +/-15% provides 81% power.

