## **7.2. Statistical Analyses**

[name] will oversee analyses, which will be conducted using Stata, SAS, or R-Language software. Preliminary analyses will assess sample characteristics (e.g., dependence, race) by treatment using t-test or contingency table methods. These variables will also be examined for their relationship to completion of outcome assessments. Variables related to treatment arm or completion of follow ups will be included as covariates in analyses of study aims. Compliance measures will be evaluated across treatment arms, and controlled for in primary analyses. We will examine the correlation between self-report and pill count data and week-5 bupropion plasma levels. We will use intent-to-treat as the primary method to evaluate study aims.

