### **7.2.2. Specific Aim 1: To compare the efficacy of bupropion with placebo for smoking cessation in pregnant smokers.**

For **H1**, we will test for treatment group differences in a binary abstinence outcome that is a repeated measure using a generalized estimating equations (GEE) model with a logit link. Quit rates at the end of week 10 of treatment and 24 weeks post-TQD will represent our primary outcome variables. Medication group (bupropion vs. placebo) and time point (end of week 10 of treatment and 24 weeks post-TQD) will be treated as categorical predictor variables, and the model will predict separate effects of treatment on abstinence at each time point (an interaction). Our initial analyses will be stratified by site, and we will carefully examine the models for differences by site, testing for an overall interaction. We will use baseline depression (PHQ-9 score of 10) to stratify the randomization. The model may include a small number of covariates added to control error or adjust for confounding [e.g., age, history of pre-term delivery, baseline gestational age, daily smoking rate]. Any variables found to be associated with both outcome and treatment assignment will be entered as covariates. In the absence of an overall interaction (by site), we will pool the study population and account for site in the model as a binary predictor. To evaluate the effectiveness of randomization, we will compare summary statistics for participant characteristics in the two study arms. If there is an imbalance in participant characteristics, statistical adjustment will be used to ensure that the initial results were not biased by it.

Because many participants will fail to become completely abstinent, but may show a reduction in smoking, we will examine cigarette consumption as a secondary outcome. The analysis will be similar to the primary analysis, except that we examine the effect of treatment arm on daily cigarette counts using a GEE model with a negative-binomial link. Likewise, time to (recurrent) event models will be fitted using Cox regression, stratified by event sequence, as in Schnoll et al. (52), to assess lapse and recovery events over 24 weeks.

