### **MEASURES FOR PARTICIPANT SAFETY.**

**Medication Adverse Events Checklist.** An adverse events checklist will assess the frequency and severity of common adverse events associated with bupropion (rated as: none, mild, moderate, or severe). This measure will be conducted at weeks 1, 3, 5, 7, and 10. This assessment is meant to monitor participant safety and reduce or stop treatment if need be. But, adverse events will be considered an outcome and a covariate in the analysis, as the overall frequency and/or as the presence (ever) of specific common adverse events. Our adverse events measure includes items that have been reported from bupropion use. In addition, we will monitor the prenatal care record to identify adverse obstetrical events, which will be recorded and reviewed regularly by the study team at each site. The data will be fully abstracted at the time of delivery for use in data analysis, which will provide a second opportunity to review obstetrical adverse events that may have occurred during the pregnancy.

**Open-ended Questions.** In addition, open-ended questions concerning adverse events are assessed at these weeks. Staff will probe for physical and psychiatric adverse events. This method is included to supplement standard adverse event measures so non expected adverse events will be captured. Events will be classified as none, mild, moderate, or severe.

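### Beyond site, the primary models have no fixed covariate list, and the plan adds compliance and adverse events, both observed after randomisation, as adjusters

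*Combined protocol and SAP*

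**What the plan says.** The rules are spread over four places in the combined protocol and SAP.

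- **Section 7.2, Statistical Analyses:** "Variables related to treatment arm or completion of follow ups will be included as covariates in analyses of study aims". No threshold is given. The same paragraph has compliance measures compared between arms and adjusted for in the primary analyses, and names intent-to-treat as the primary method.
- **Section 7.2.1, Missing Data:** variables associated with missingness at p < 0.05 become covariates in the analyses of the aims. A completers-only analysis is also planned.
- **Section 7.2.2, Specific Aim 1:** "Any variables found to be associated with both outcome and treatment assignment will be entered as covariates". Just before this, the text permits, but does not require, a few covariates to reduce error or confounding. Its examples are age, previous preterm delivery, gestational age at baseline and daily smoking rate. Observed imbalance also triggers adjustment. Site enters as a binary term if there is no site interaction. The PHQ-9 cut-off stratifies the randomisation but is not said to be in the model.
- **Section 10.1, Measures for Participant Safety:** "adverse events will be considered an outcome and a covariate in the analysis".

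For size, section 7.1.1 plans the week-10 comparison on "placebo = 21.2%; bupropion = 35.9%, OR = 2.1; ref. 44" and states that "A sample of 360 provides 88% power to detect a significant between-group effect".

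**The concern.** Two different problems sit under these rules.

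The first is selection. Under randomisation, an association between a baseline variable and arm is chance. A rule keyed to it rarely picks up a given strong predictor of quitting, and the primary model is unknown until the data have been seen. The rules also differ among themselves: section 7.2 admits a variable on its relation to arm alone, while section 7.2.2 needs arm and outcome together. Two analysts following the plan could fit different primary models.

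The second is timing. Compliance and adverse events arise after randomisation and can be affected by the drug. Section 3.2 says that adverse effects may lead to dose reduction or suspension, which links the two. Conditioning on such a variable removes the protection of randomisation. The adjusted contrast is then no longer the intent-to-treat effect, and it can be biased in either direction.

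**Working it through.** **1. The plan's own figure.** Inputs are 180 per arm (section 5.3), quit rates 0.212 and 0.359 (section 7.1.1), and two-sided alpha 0.05 (section 7.1). For a pooled z-test:

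- mean rate = (0.212 + 0.359)/2 = 0.2855
- SE under the null = √(2 × 0.2855 × 0.7145/180) = 0.0476
- SE under the alternative = √[(0.212 × 0.788 + 0.359 × 0.641)/180] = 0.0470
- power = Φ[(0.147 − 1.96 × 0.0476)/0.0470] = Φ(1.14) = 87.3%

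The unpooled version gives 87.9%. The stated 88% reproduces, and it is an unadjusted figure.

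**2. Selection of one baseline covariate.** Simulation of 20,000 trials per setting: logistic model at one time point, marginal rates held at 21.2% and 35.9%, one standardised covariate. The documents give no covariate strengths, so a range is assumed. Selecting on arm alone and on arm plus outcome, each at p < 0.05, gave the same results.

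| Assumed covariate OR per SD | Power, never adjusted | Power, selected | Power, pre-specified | Type I error, selected |
|---|---|---|---|---|
| 1.65 | 87.4% | 87.5% | 88.6% | 4.6% |
| 2.7 | 87.3% | 87.8% | 91.9% | 4.7% |
| 4.5 | 87.5% | 88.5% | 95.2% | 4.3% |

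The covariate enters in only about 5% of trials. Against pre-specified adjustment the gap is about 1, 4 or 7 points.

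**3. Several candidates.** Ten baseline candidates, three of them prognostic at log-OR 0.6 per SD (assumed), with the same marginal rates and 4,000 trials. The arm-and-outcome rule adds something in about 16% of trials and gives about 88–89% power. Always including the three predictors gives about 93%. Type I error under the rule is about 4.7%.

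**4. How unsettled the model is.** If k independent baseline variables are screened against arm at 0.05, the chance that at least one is flagged is 1 − 0.95^k: 23% for k = 5, 40% for k = 10, 64% for k = 20.

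**5. Adjusting for compliance.** Assumed set-up: a latent factor U (for example motivation) has log-OR 1 per SD on abstinence and correlation 0.6 with compliance within arm; compliance has no effect of its own on abstinence; the arms differ in mean compliance by a set amount. Without the compliance term, rejection is about 5% under no effect and 87% at the planned rates, with log-OR 0.74. With it:

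| Compliance, bupropion minus placebo (SD) | Rejection, no true effect | Rejection, planned rates | Mean log-OR, planned rates |
|---|---|---|---|
| −0.6 | 21.0% | 99.0% | 1.11 |
| −0.4 | 12.4% | 97.9% | 1.00 |
| −0.2 | 7.0% | 95.0% | 0.89 |
| 0 | 5.0% | 89.0% | 0.78 |
| +0.2 | 7.1% | 78.0% | 0.68 |
| +0.4 | 12.7% | 62.1% | 0.57 |
| +0.6 | 22.2% | 43.2% | 0.46 |

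The high rejection rates in the upper rows reflect upward bias, not better power. No corresponding calculation was made for adverse events. The mechanism is the same in kind, but its size here is not known.

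**The case against.** Much can be said for the plan, and several stronger readings fail.

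- **That the trial falls short of its stated power.** A reader might infer this, because a simulation that treats the OR of 2.1 as conditional on three covariates gives about 78% under the rule and 84% with pre-specification. That set-up implies marginal quit rates of about 25% and 38%, not those in section 7.1.1. At the planned rates the rule meets 88%. What is lost is an available gain, whose size is assumed.
- **That the selection rule inflates type I error.** With baseline variables it does not; the error is 4.3% to 4.7%.
- **That strong predictors are left out by design.** The plan allows prognostic covariates with no imbalance condition. The fair criticism is that they are discretionary.
- **That covariates are chosen on outcome alone.** No rule does this, and site is a genuine exception to the lack of fixed terms.
- **That the sentence in 7.2.2 itself brings in post-randomisation variables.** It fails to exclude them, but the nearby wording on sample and participant characteristics most naturally means baseline.
- **That section 10.1 puts adverse events in the H1 model.** It sits among safety procedures and does not name the primary model.

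All of this stands as a limit on the point. It does not answer the compliance instruction in section 7.2, which names the primary analyses. Section 10.1 leaves the role of adverse events open, and for H2 they are the outcome itself.

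**Conclusion.** The point holds in two parts of unequal weight.

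The lesser part is efficiency and transparency. The primary model is not determined in advance beyond site, and selection on chance imbalance gives up roughly 1 to 7 points of power against pre-specified adjustment. This rests on assumed covariate strengths and a one-time-point simplification of the GEE.

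The greater part is validity. It rests first on the compliance instruction in section 7.2 and second on the adverse-event sentence in section 10.1. Followed as written, the compliance instruction can bias the H1 estimate. The 7% to 22% type I error is an illustration under the stated latent-factor assumption and compliance differences of 0.2 to 0.6 SD. With no difference between arms the error stays at 5%. The documents do not predict that difference, so this is a risk, not a forecast. It should be corrected, because the plan gives no assurance that the arms will be alike in compliance.

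**What to change.** Before unblinding, amend section 7 and the sentence in section 10.1 as follows.

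1. For the primary H1 to H3 models, replace the association-based rules in 7.2, 7.2.1 and 7.2.2 by a short fixed list of baseline variables already collected: site, PHQ-9 stratum, and a few prognostic ones such as age, daily smoking rate, FTND and gestational age. Add history of preterm delivery for birth outcomes. The exact prognostic variables are for the sponsor to choose; fixing them in advance is what matters.
2. State that compliance, adverse events and every other post-randomisation variable are excluded from those models and appear only in labelled supportive analyses.
3. Keep adjustment for correlates of missingness in the completers-only sensitivity analysis, where it has a legitimate role.

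The cost is SAP wording, with no new data and no change in sample size. The team gives up discretion to adjust the primary model for imbalances seen later, but can report such an adjustment as a sensitivity analysis.

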### 5.3. Method for Assigning Participants to Treatment Groups

Participants will be randomly assigned to one of two treatment conditions: Bupropion 300 mg/day (n = 180) or placebo (n = 180). We will use small-block randomization by site (Penn or MATER) provided by [name], the study biostatistician. A PHQ-9 score of 10 or greater will be used to identify major depression and stratify the randomization on it. Study site (Penn or MATER) will be the second of the two stratification variables. Study staff and the Investigational Drug Service (IDS) staff will be responsible for medication randomization. The process for randomization is: 1) The research coordinator will complete a “randomization form,” which includes the variables to be entered into the randomization program and fax or email the form without protected health information to the UPenn site; 2) A designated study staff member

Table 1: Medication Dispensing Schedule

	Medication Dispensed For	Morning Dose	Evening Dose	Total Daily Dose
Visit A: Screening	N/A	No medication	No medication	
Visit B: Baseline	Wk 1	150 mg	No medication (for first 3 days); then 150 mg	150 mg
Visit C: Wk 1	Wk 2 through Wk 5	150 mg	150 mg	300 mg
Visit D: Wk 3	N/A	N/A	N/A	N/A
Visit E: Wk 5	Wk 6 through Wk 10	150 mg	150 mg	300 mg
Visit F: Wk 7		150 mg	150 mg	300 mg
Visit G: Wk 10	Endpoint	No medication	No medication	N/A

CONFIDENTIAL

This material is the property of the University of Pennsylvania. Do not disclose or use except as authorized in writing by the study sponsor

Visit H: Wk 24 Post-TQD	N/A	No medication	No medication	N/A
Visit I: 2 wk postpartum	N/A	No medication	No medication	N/A
Visit J: 6 wk postpartum	N/A	No medication	No medication	N/A

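### The primary H1 analysis pools the sites only if a site-interaction test with no stated level finds nothing, and the plan names no primary estimate otherwise

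*Combined protocol and SAP*

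**What the plan says.** Section 7.2.2 introduces the H1 model, a GEE for abstinence at week 10 and at week 24 post-TQD. It then sets an order of work: "Our initial analyses will be stratified by site, and we will carefully examine the models for differences by site", with a test for an overall site interaction. The next step is conditional: "In the absence of an overall interaction (by site), we will pool the study population", with site then entered as a binary predictor.

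Three things are not stated there or elsewhere:
- the significance level of the interaction test;
- the primary estimate, alpha and success rule for H1 if an interaction is found;
- that the pooled test is primary whatever the interaction shows.

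The Study Summary describes the same GEE treatment test with no site step. Section 7.1.1 bases power on everyone randomized: "A sample of 360 provides 88% power to detect a significant between-group effect". Both presume one pooled test. Section 5.3 stratifies randomization by site (Penn or MATER) and by PHQ-9 score.

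**The concern.** As written, whether the pooled comparison is the primary analysis is decided by a test on the outcome data. Two problems follow.

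First, an interaction test rejects at its own level even when the treatment works equally well at both sites. Some trials would lose the pooled test by chance.

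Second, what happens next would have to be settled after the site results are known. That is a data-driven choice of primary analysis. Depending on the rule chosen, it can cost power or raise type I error.

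The pre-test would offer little in return if it seldom detects a real site difference of plausible size.

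**Working it through.** **Inputs from the plan.** Quit rates at week 10: "placebo = 21.2%; bupropion = 35.9%, OR = 2.1; ref. 44" (7.1.1). 180 per arm (5.3). Two-sided tests at alpha 0.05 (7.1). Missing smoking outcomes count as smoking (7.2.1), so all 360 are analysed. Two site strata (5.3).

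**Assumptions, because the plan is silent.** Interaction level 0.05, range to 0.20. Site split 50:50, varied to 80:20. One time point.

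**1. The plan's own figure.** With p1 = 0.212, p2 = 0.359, mean 0.2855 and n = 180 per arm:
- SE under the null = √(2 × 0.2855 × 0.7145 / 180) = 0.0476
- SE under the alternative = √((0.212 × 0.788 + 0.359 × 0.641) / 180) = 0.0470
- Power = Φ((0.147 − 1.96 × 0.0476) / 0.0470) = Φ(1.14) = 87.3%

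With the unpooled SE throughout, power is 87.9%. The stated 88% is reproduced.

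**2. Loss of the pooled test by chance.** If effects are equal, the pre-test rejects at its own level: 5% at 0.05, 10% at 0.10, 20% at 0.20. If it were run separately at the two time points at 0.05, the rate under independence would be 1 − 0.95² = 9.75%. It is lower given the plan's stated correlation above 0.7.

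**3. Probability of a significant pooled result.** The pre-test and the pooled test are close to independent, so this is roughly power × (1 − interaction level):
- 0.05: 0.873 × 0.95 = 83%
- 0.10: 0.873 × 0.90 = 79%
- 0.20: 0.873 × 0.80 = 70%

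A simulation of the two-step procedure agrees. It used 400,000 trials per scenario, Wald tests on log odds ratios, and a site-stratified pooled test. At a 50:50 split it gives 83%, 78% and 70%, against 87% for the pooled test run unconditionally.

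**4. Type I error if either site may carry H1.** This rule is hypothetical. With both arms at 21.2% and a 50:50 split:

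| Interaction level | Pre-test rejects | Either site significant, given rejection | Pooled significant, given no rejection | Overall type I error |
|---|---|---|---|---|
| 0.05 | 4.76% | 62.8% | 4.42% | 0.0476 × 0.628 + 0.9524 × 0.0442 = 7.2% |
| 0.10 | 9.71% | 46.3% | 4.56% | 0.0971 × 0.463 + 0.9029 × 0.0456 = 8.6% |

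Across splits from 50:50 to 80:20 the ranges are about 7.0–7.3% and 8.1–8.6%. The always-pooled test gives 4.4% in the same simulation.

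**5. Power of the pre-test.** Take odds ratio 2.08 (log 0.733) at one site and 1.0 at the other, 90 per arm at each:
- Variance of the log odds ratio, first site = 1/(90 × 0.1671) + 1/(90 × 0.2301) = 0.1148
- Second site = 2/(90 × 0.1671) = 0.1330
- SE of the difference = √0.2478 = 0.498
- Power at 0.05 = Φ(0.733/0.498 − 1.96) = Φ(−0.49) = 31%

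At an 80:20 split it is 21%. For 80% power at 50:50, the ratio of the two odds ratios must be about exp((1.96 + 0.84) × √(2 × 0.1148)) = 3.8.

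**6. After a chance rejection under the planned effect.** At 50:50 and level 0.05, each site is significant about 51% of the time, at least one 99%, both 3%. What is lost therefore depends almost entirely on the success rule, which the plan does not give.

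**The case against.** The strongest reply is that the text is loose drafting and not a rule that removes the primary test. The Study Summary and the opening of 7.2.2 state the GEE comparison with no site condition, and the pooling sentence may only describe how site enters the model. It also speaks of the absence of an interaction, not of a non-significant one. In part this stands: a significance threshold is an inference. But the plan does say that it will test for the interaction, and it makes pooling follow from the result. No section makes the pooled analysis unconditional.

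There is also a clinical reason to look at the sites. Methadone-maintained smokers are enrolled at MATER (4.3), so the strata may differ in response. That justifies reporting site-specific results. It does not justify leaving the primary analysis open.

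Three stronger readings are tempting, and the documents do not support them.
- A reader might infer that H1 falls back on separate site tests. The plan does not say so. One could equally keep all 360 in one model with a site-by-treatment term and report an averaged effect.
- A reader might set 88% against within-site power of about 60% (90 per arm) or 44% (60 per arm) and call the gap the loss. Those are unconditional powers at splits the plan does not give, not power after the pre-test rejects (step 6). The whole-trial loss at an interaction level of 0.05 is about 4 points.
- A reader might conclude that the 88% is wrong. It is right for the pooled test.

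**Conclusion.** The concern holds as a gap in the definition of the primary analysis, of modest size by chance alone. At an interaction level of 0.05, about 1 trial in 20 would lose its pooled test even with equal site effects, and the probability of a significant pooled result would fall by about 4 points. At 0.20 these become 1 in 5 and about 17 points. The more important defect is that both the threshold and the consequence of crossing it are undefined. One natural way to fill the gap afterwards, accepting either site, would take type I error above 5%.

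The figures rest on the plan's week-10 quit rates, one time point and assumed interaction levels. The type I error and pre-test power figures also rest on assumed site splits. The either-site rule is an illustration and not something the plan proposes.

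**What to change.** In 7.2.2, state that the pooled GEE adjusted for the site stratum is the primary H1 analysis in all cases. State that the site-by-treatment interaction and the site-specific estimates will be reported as supportive. Because randomization is stratified by site, the pooled comparison is a valid test of the average effect whether or not effects differ. Power stays at about 87% with the same 360 women.

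The site variable should be defined in the same edit: 5.3 uses two strata, while the Study Summary lists more centers.

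The cost is a sentence or two, to be added before unblinding. The downside is that, if effects truly differ, the primary result is an average and must be read with the site-specific estimates. A smaller repair is to keep the pre-test but state its level and name the estimate and success rule if it rejects. That closes the gap in definition, but the primary analysis still depends on the data.

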### **Potential Risks**

The most common adverse events associated with bupropion when used for smoking cessation are dry mouth (11%), insomnia (31%) and dizziness (8%).

Frequent adverse reactions (occurring in at least 1% of patients) include rhinitis, neck pain, allergic reaction, hot flashes, hypertension, increased appetite, anorexia, constipation, arthralgia, myalgia, tremor, somnolence, thinking abnormality, bronchitis, pruritis, rash, dry skin, urticaria, taste perversion, asthenia, fever, headache, dyspepsia, vomiting, agitation, depression, irritability sweating, blurred vision or diplopia, and urinary frequency (Zyban Package Insert).

Infrequent adverse reactions (occurring in less than 1% but greater than 0.1% of patients) include: chills, inguinal hernia, photosensitivity, flushing, migraine, postural hypotension, stroke, tachycardia, vasodilation, abnormal liver function, bruxism, dysphagia, gastric reflux, gingivitis, jaundice, stomatitis, ecchymosis, edema and peripheral edema, leg cramps and twitching, abnormal coordination, CNS stimulation, confusion, decreased libido, decreased memory, depersonalization, emotional lability, hostility, hyperkinesia, parkinsonism, hypertonia, hypesthesia, paresthesia, suicidal ideation, and vertigo, accommodation abnormality and dry eye, polyuria, and urinary urgency (Zyban Package Insert).

Rare adverse reactions (occurring in less than 0.1% of patients) include: malaise, syncope, amnesia, ataxia, derealization, hypomania, and bronchospasm (Zyban Package Insert).

Bupropion is contraindicated in patients with a history of seizure disorder or in patients with a current or prior diagnosis of bulimia or anorexia, because of a higher incidence of seizures in these individuals when treated with bupropion.

Patients taking bupropion for smoking cessation have experienced mood changes, including depression or mania, psychosis, hallucinations, paranoia, delusions, homicidal ideation, hostility, agitation, aggression, anxiety, and panic, as well as suicidal ideation, suicide attempt, and completed suicide.

Abuse potential: Bupropion is not likely to be reinforcing to users of stimulants, including amphetamines. Abuse of bupropion by inhalation or injection of crushed tablets have been reported, resulting in seizures and/or death.

The risk of bupropion for smoking cessation in pregnant women has not been adequately evaluated. There is a risk that bupropion could adversely affect the developing fetus.

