**H2:** We will compare treatment arms for equivalence of the frequency of moderate-to-severe AEs (individual and total). The hypothesis test for equivalence is a test of whether the OR is out of the prescribed range for the difference between the treatment arms. Using logistic regression, we will conduct two one-sided tests against predefined upper and lower equivalence boundaries on percent reporting only mild AEs. The test-statistic will be the z-score corresponding to the log of the OR. This provides a more valid test of the potential safety of bupropion for pregnant smokers than a simple comparison of mean responses on a measure of AEs.

**H3:** Mean birth weight will be compared for treatment groups using a two-sample t-test, in the context of multiple linear regression. The regression format allows us to add covariates to adjust for imbalances in participant characteristics between treatment arms. Treatment will be entered as a binary indicator. In a secondary analysis, we will also compare the percentage of participants in each group that delivers an infant of LBW (1500-2500 g) or preterm delivery. These secondary hypotheses will be tested using the z-score corresponding to the OR that will be estimated using logistic regression.

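### H2 plans equivalence tests for individual AEs and birth outcomes without giving them margins; the only windows, 15 points either side of overall AE proportions, do not work for uncommon events

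*Combined protocol and SAP*

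**What the plan says.** Section 7.2.2 (H2) sets the scope of the equivalence analysis: "We will compare treatment arms for equivalence of the frequency of moderate-to-severe AEs (individual and total"). The test is two one-sided tests by logistic regression, using the z-score of the log odds ratio. The boundaries are called predefined and are described on the percentage of participants reporting only mild AEs. No number is given there.

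The numbers are in the power section, 7.1.1. The first scenario cites earlier data in which "45% of bupropion-treated participants reported no moderate-to-severe AEs, vs. 47% of participants on placebo, a 2% difference". It claims that "we will have 82% power to detect similar equivalence between treatment arms on the frequency of moderate-to-severe AEs over the course of the trial", "using an equivalence window of 0.30 to 0.60". The second scenario puts both arms at 30% with a window of plus or minus 15% and claims 81% power. Section 7.1 adds that "Equivalence testing was approximated as two one-sided tests", at 0.025 each.

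The H2 paragraph of Section 7.1.1 also covers the infant and the pregnancy: "Key birth outcomes will include Apgar scores, birth weight, duration of pregnancy, rate of obstetrical complications, and need for NICU admission". It then says that these analyses will involve a test of equivalence. Birth weight, low birth weight and preterm delivery have ordinary difference analyses under H3 in Section 7.2.2. NICU admission and obstetrical complications have none.

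**The concern.** Both windows describe the share of women with or without any moderate-to-severe AE, a proportion between about 30% and 55%. The AE checklist in Section 10.1 has 39 numbered items, and most single events will be far less common. An analyst who reaches the individual-AE tests must use the 15-point window, convert it to an odds ratio, or choose a margin later. The first can label a multiplied harm equivalent. The second can fail arms that are identical. The third leaves the margin open to choice after the data are seen.

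Section 7.1.1 itself argues that a non-significant difference does not show safety, and Section 1.5 says the risk in pregnant women has not been adequately evaluated. An equivalence statement about a single harm would therefore be read as a safety claim.

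**Working it through.** **Inputs.** 180 per arm (Section 5.3); two one-sided tests at 0.025 (Section 7.1); the two windows in Section 7.1.1. The documents give no rates for individual moderate-to-severe AEs or for NICU admission, so the rates below are assumed. For orientation, Section 1.5 gives 8% (dizziness), 11% (dry mouth) and 31% (insomnia). Those rates are not limited to moderate-to-severe events, which would be rarer.

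**The plan's own power figures.** With SE = sqrt[p0(1-p0)/180 + p1(1-p1)/180], the chance of passing is Φ((0.15 - 1.96·SE - d)/SE) - Φ((-0.15 + 1.96·SE - d)/SE), where d = p1 - p0. For 47% against 45%, SE = 0.0525 and power is 60%. With no true difference it is 63%, and on the odds-ratio scale 66-68%. The stated 82% is not reproduced. For 30% in both arms the result is 75% (risk difference) or 77% (odds ratio), against a stated 81%. This is a separate matter from the present point, which does not depend on it.

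**Window as a 15-point risk difference, uncommon events.** Example, 2% to 10%: SE = sqrt[(0.0196 + 0.0900)/180] = 0.0247 and 1.96·SE = 0.0484. Then (0.15 - 0.0484 - 0.08)/0.0247 = 0.88, and Φ(0.88) = 0.81; the second term is negligible. Exact binomial enumeration is alongside.

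| True rates (placebo, bupropion) | Ratio | Declared equivalent, normal | Exact |
|---|---|---|---|
| 2%, 10% | 5.0 | 81% | 79% |
| 3%, 15% | 5.0 | 17% | 20% |
| 5%, 10% | 2.0 | 95% | 94% |
| 8%, 16% | 2.0 | 54% | 55% |
| 10%, 15% | 1.5 | 82% | 82% |
| 10%, 20% | 2.0 | 27% | 28% |

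The largest ratio inside the margin is (p + 0.15)/p: 8.5 at 2%, 5 at 3.75%, 4 at 5% and 2.5 at 10%.

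**Window as odds-ratio limits.** Measured from 45% event-free, 0.30 to 0.60 is an odds ratio of 0.52 to 1.83 for being event-free. For having an event it is the reciprocal, 0.55 to 1.91 (log limits -0.606 and 0.647). Measured from 30%, 15% to 45% is 0.41 to 1.91 (log limits -0.887 and 0.647). With identical arms at incidence p, SE(log OR) = sqrt[2/(180·p(1-p))]. At 8% this is 0.389, so the interval half-width is 0.762. The widest half-width that fits window 1 anywhere is (0.606 + 0.647)/2 = 0.626. For window 2 it is (0.887 + 0.647)/2 = 0.767.

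Chance of showing equivalence with identical arms, normal approximation (exact):

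| True incidence | Window 1 | Window 2 |
|---|---|---|
| 5% | 0% (0%) | 0% (below 0.1%) |
| 8% | 0% (0%) | 1% (4%) |
| 11% | 0% (1%) | 23% (22%) |
| 15% | 13% (12%) | 44% (43%) |
| 20% | 32% (31%) | 61% (60%) |
| 31% | 57% (56%) | 78% (78%) |

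Enumerating every pair of counts, nothing passes window 1 with fewer than 25 placebo events (25/180 = 13.9%), and nothing passes window 2 with fewer than 17 (17/180 = 9.4%).

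**The case against.** The strongest reply is that the plan never says these windows govern single events. They are power assumptions for an overall proportion, and Section 7.2.2 refers only to predefined boundaries without figures. That is correct. What is written is a planned test with no margin; carrying the windows over is an inference from the absence of any other.

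A reader might infer several stronger things that the documents do not support:

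- **One window, set for a 45% event rate.** There are two windows, and 45% is the event-free share, so about 55% have an event.
- **A fivefold rise generally passes.** It lies inside 15 points only when the placebo rate is below 3.75%, and it is likely to pass only at about 2% or less.
- **A doubling of NICU admission would be certified.** From an assumed 10%, a doubling passes in about 28% of trials. The 82% figure belongs to a 1.5-fold rise.
- **The odds-ratio version can never be met.** It fails only for uncommon events, and the threshold depends on the window. At 11% the exact chance is 1% or 22%.

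The birth-outcome scope is also ambiguous. H2 in Section 2 and the H2 analysis in Section 7.2.2 name only AEs, and a percentage window has no meaning for birth weight or duration of pregnancy. Individual harms are also watched through severity coding, SAE reporting and the DSMB, independently of H2. Finally, margins specified for each event would be another remedy.

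These arguments lower the severity. They do not supply a margin, and they leave the individual-AE test in the analysis section.

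**Conclusion.** The point holds in limited form. The plan commits to equivalence tests for individual moderate-to-severe AEs, and in Section 7.1.1 for birth outcomes, without a margin for any of them. If the 15-point windows are carried over, the test is too lenient for uncommon events as a risk difference and close to or fully unattainable as an odds ratio. The calculations rest on that carry-over, on assumed event rates, on 180 evaluable women per arm and, for window 1, on measuring the limits from 45%. If the carry-over is rejected, what remains is a set of planned tests whose margin could be chosen after the data are seen. This should be corrected before analysis, but it does not undermine the trial.

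**What to change.** In Section 7.2.2, delete 'individual and' so that the formal equivalence test covers only total moderate-to-severe AEs. In Section 7.1.1, limit the equivalence sentence to that total.

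For each individual AE, and for NICU admission and obstetrical complications, report both rates, the risk difference and the risk ratio with 95% confidence intervals (exact where events are sparse). State that no equivalence claim will be made from them. Birth weight, low birth weight and preterm delivery keep their H3 analyses.

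The boundary for the total, with its number and scale, still has to be written into Section 7.2.2.

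The cost is wording only: no extra participants, visits or data. The sponsor gives up equivalence claims for single events, which a trial of this size could not support.
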